9.7.2.2.4 Subgroup Analysis

Analyses will be undertaken for the study population as a whole and by relevant blinatumomab consolidation and chemotherapy consolidation subgroups. Dependent on the numbers of patients enrolled, there may be additional subgroups of interest. These subgroups may include the following (additional subgroups may be investigated):

- Age at treatment with SOC/blinatumomab by age categories 0-2 years, 3-6 years, 7-12 years, 13-18 years
- Patients who were MRD+ at any point in the first three years following initial alloHSCT
- Patients who experienced acute GvHD following initial alloHSCT
- Patients who experienced neurological, endocrine or immune events in the first three years following alloHSCT (primary outcomes only).
- Patients with different indications for blinatumomab: EU indication (paediatric patients aged 1 year or older with Ph- B-cell precursor ALL which is refractory or in relapse after receiving at least 2 prior therapies or in relapse after receiving prior alloHSCT) vs. non-EU indication (eg, relapsed ALL after receiving only 1 prior therapy, ALL with MRD, Ph-positive relapsed, or refractory ALL or high-risk first relapse ALL).

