This study (Study 20180130) will provide the opportunity to investigate the long-term safety profile in paediatric patients with respect to known short-term toxicities of blinatumomab, eg, those related to the immune, neurologic, and HSCT-related events. The study will involve long-term follow-up of both chemotherapy- and blinatumomab-treated paediatric patients who then undergo alloHSCT. Patients who have undergone alloHSCT following treatment with either blinatumomab or standard of care (SOC) chemotherapy will be invited to participate in the 20180130 study.

Study 20180130 will provide the opportunity to investigate the long-term safety profile of blinatumomab, by providing 12 years of follow-up of patients treated with either blinatumomab or chemotherapy, followed by alloHSCT (follow-up commencing at transplantation). The study will investigate neuropsychomotor developmental impairment, endocrine impairment, neurological impairment, and immune system impairment.

- Research Question and Objective(s)
 - Primary Objective

(1) To estimate incidence of neuropsychomotor developmental impairment, endocrine impairment, neurological impairment, and immune system impairment (including auto-immune disorders and vaccine failure)

- Secondary Objectives
 - (1) To estimate the incidence of HSCT related adverse events (AEs)
 - (2) To estimate the incidence of subsequent relapse of leukemia including in the CNS
 - (3) To estimate the cumulative incidence of long-term AEs
 - (4) To estimate the incidence of secondary malignant formation
 - (5) To estimate overall survival
- Hypothesis Estimation
 - The study will compare blinatumomab therapy versus chemotherapy treatment

for the occurrence of neuropsychomotor developmental impairment, neurological impairment, endocrine impairment, and immune system impairment.

• Study Design/Type

This study is a prospective observational study.

• Study Population or Data Resource

Paediatric patients who have undergone alloHSCT following treatment with either blinatumomab or SOC chemotherapy will be invited to participate in the study.

• Summary of Patient Eligibility Criteria

Inclusion Criteria

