9.2.1 Study Period

Enrolment of patients into 20180130 will occur if they meet all eligibility criteria. All eligible patients or their caregivers/legal guardians will be approached to provide informed consent for participation. Once informed consent has been given, and all inclusion/exclusion criteria are met, the patient will be enrolled via interactive response technology (IRT) in the study and data collection will begin. The study will commence at the first data collection of the first site. Patients will be followed for a maximum of a 12-year period or up to the age of 25 years, death, withdrawal of consent, or loss to follow-up, whichever comes first. The study will end when 12 years of follow-up for the last patient (if the patient has not withdrawn consent, been lost to follow-up, or died before the end of the 12 years of follow-up) is completed. If the last patient enrolled on study dies or is lost to follow-up before the 12 years following alloHSCT, the remainder

of the patients on study will continue to be followed until all patients on study have reached 12 years following alloHSCT, until death, withdrawal of consent, or lost to follow-up, whichever occurs first.

Data will be entered into an eCRF and will encompass information abstracted from patient charts from routine clinical visits. Data abstraction will be performed approximately every 6 months (± 30 days) starting at enrolment. Additional data on neuropsychomotor development will be assessed through specific questionnaires (paper and/or electronic) which will be administered at pre-specified intervals starting at enrolment (approximately every 6 months [± 30 days] for patients up to 6 years old and approximately yearly [± 60 days] for patients from 6 years old).

The first day of follow-up (day 1) will be the date of successful completion of alloHSCT (following chemotherapy/ blinatumomab treatment).

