9.2.5 Study Follow-up

This is a prospective study where data will be collected at routine clinical visits which will occur per standard of care (for a period of up to 12 years). A total of 12 years follow-up or 144 months of follow-up is planned for study 20180130. At each data collection stage, relevant information will be retrieved from patient charts subsequent to the preceding data abstraction time point to ensure there is no gap in data collection. Data abstraction will be performed approximately every 6 months (± 30 days) starting at enrolment. Additional data on neuropsychomotor development will be assessed through specific questionnaires (paper and/or electronic) which will be administered at pre-specified intervals starting from enrolment (approximately every 6 months [± 30 days] for patients up to 6 years old and approximately yearly [± 60 days] for patients from 6 years old). For each enrolled patient, data collection will end at 12-years of follow-up, the age of 25 years, loss-to-follow-up, withdrawal of consent, or death, whichever occurs earliest. All treatments for ALL will be captured in this period.

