9.3 Variables

9.3.1 Outcome Assessment

Primary Objective

- Impairment is defined as any of the following:
 - o Neuropsychomotor development impairment in the areas of:
 - Social and emotional
 - Language/communication
 - Cognitive (learning, thinking, problem-solving)
 - Motor (both gross and fine motor development)
 - As lower scores on adaptive functioning measures indicate greater deficits (ie, lower day-to-day functioning), impairment will be defined as performance falling 2 or more standard deviations below the normative population mean in 1 or more adaptive functioning domain(s) (ie, motor, language, social skills).

- As higher scores on executive function (ie, cognitive) measures indicate greater deficits (ie, more problematic thinking), impairment will be defined as performance falling 2 or more standard deviations above the normative population meant in 1 or more executive function domain(s). For motor skills of patients ages 10 years and older, impairment will be defined as having an age-equivalency a year or more below their chronological age, as further development is not expected beyond that age and normative data is limited.
- Individual change over time across domains will also be assessed for significance. Specifically, it is anticipated that patients will have their own respective baseline level of skills across assessed areas. For example, some individuals may have significantly above average day-to-day functioning and/or cognitive skills at the start of the study. Thus, the formal definition of psychomotor 'impairment,' placing two or more standard deviations below the mean, will not capture meaningful changes amongst these patients. To account for this, analysis will also examine statistically significant changes over time within each person's own scores across psychomotor domains. Changes that are two or more standard deviations from one's own baseline will be considered relevant adverse effects.

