9.3.2 Covariate Assessment

Baseline

- Recording of ALL-related diagnoses history both prior to and following blinatumomab/SOC chemotherapy
 - Disease status (prior to blinatumomab/SOC chemotherapy)
 - MRD status (following treatment; MRD positivity defined at a level $\ge 10^{-4}$ in PCR and/or flow quantification)
 - Relapse (following treatment)
 - Time point of relapse (time since primary diagnosis and time after completion of primary therapy)
 - Whether extramedullary relapse
 - Bone marrow status at relapse
 - Secondary malignancy (following treatment)
- Recording of ALL-related treatment history
 - Details of SOC-chemotherapy therapy
 - Specific therapy
 - Duration of therapy
 - Details of blinatumomab therapy
 - Number of blinatumomab cycles
 - Occurrence of further blinatumomab therapy following initial discontinuation
 - Duration of blinatumomab therapy
- Recording of alloHSCT status
 - Occurrence of alloHSCT
 - Interval between SOC-chemotherapy/blinatumomab and alloHSCT
- Clinically relevant events prior to initiation of therapy or after initiation of therapy and before alloHSCT (see definitions above)
 - Neurological event
 - Endocrine event (including evidence of growth delay)
 - o Immune event
 - Toxicity (gastrointestinal, hematologic, dermatology, cardiac, pulmonary, hepatic, renal, infection, skeletal, etc.: see definitions above)
- Other important clinical factors
 - o Comorbidity
 - Concomitant medication
 - Prenatal development
 - High-risk pregnancy
 - Delivery complications including hypoxia
 - o Gestational time at the delivery
 - APGAR score
 - o Gestational weight (intrauterine growth restriction [IUGR])
 - Psychomotor development impairment and psychiatric conditions recognised prior to the therapy
- Pregnancy and breastfeeding status after blinatumomab initiation

Follow-up

- Demographics and clinical characteristics including comorbidity
 - All treatments for ALL
 - Pregnancy and breastfeeding status

- Recording of further ALL-related treatment history
 - Details of SOC-chemotherapy therapy: specific therapy, and; duration of therapy
 - Details of blinatumomab therapy: number of cycles; occurrence of further blinatumomab therapy following initial discontinuation, and; duration of therapy
- Further HSCT
 - Occurrence of HSCT
 - o Interval between SOC-chemotherapy/blinatumomab and HSCT
 - Outcome of HSCT: early/late GvHD; infection; HSCT-related toxicity (see definitions above)

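### An optional subgroup is selected on three of the four primary outcome domains inside the outcome window, so its composite incidence is 100% by construction and its domain incidences are inflated

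*Protocol*

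**What the plan says.** Section 9.7.2.2.4 plans analyses for the whole population and by treatment group. It then adds further candidates, depending on enrolment: "These subgroups may include the following (additional subgroups may be investigated". Two of the listed items are "Patients who experienced neurological, endocrine or immune events in the first three years following alloHSCT (primary outcomes only" and "Patients who were MRD+ at any point in the first three years following initial alloHSCT". A third is patients with acute GvHD after the first transplant.

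The outcome clock is set in Section 9.2.1: "The first day of follow-up (day 1) will be the date of successful completion of alloHSCT". Section 9.2.5 gives its length: "A total of 12 years follow-up or 144 months of follow-up is planned for study 20180130".

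The primary objective (Abstract and Section 8.1) is "To estimate incidence of neuropsychomotor developmental impairment, endocrine impairment, neurological impairment, and immune system impairment". Section 9.3.1 introduces these four domains with "Impairment is defined as any of the following". Section 9.7.2.2.3 asks for incidence proportions and Kaplan-Meier time to first onset for each specified event. It also provides for a logistic comparison of the treatment groups, and it censors events after relapse or secondary malignancy.

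Section 9.3.2 separately collects, as baseline covariates, "Clinically relevant events prior to initiation of therapy or after initiation of therapy and before alloHSCT (see definitions above"; the types listed there include neurological, endocrine and immune events.

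**The concern.** A subgroup should be fixed by information available before the outcome is counted. Here the qualifying events are neurological, endocrine or immune, they must fall in years 0-3 after transplant, and they belong to the impairments the study counts from transplant onward. Section 9.7.2.2.4 sets no year-3 starting point, does not restrict the analysis to later events, and does not set aside the event that qualified the patient.

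Two misreadings could follow. First, a high incidence in the subgroup could be taken to show that early events predict impairment, when selection alone produces it. Second, a comparison of blinatumomab with chemotherapy inside the subgroup conditions on something that happens after treatment and that treatment may affect. On the composite, it leaves nothing to compare. The study is a regulatory safety commitment on these same outcomes, so such figures could reach the final report.

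**Working it through.** The protocol gives no figure for this subgroup, so there is none to reproduce. The check is mainly logical, with an illustration for the single domains.

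**1. Windows.** The outcome window runs from day 1 (alloHSCT) to at most 144 months. The qualifying window is months 0 to 36. It lies wholly inside the outcome window.

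**2. Overlap of definitions.** The primary domains are neuropsychomotor, neurological, endocrine and immune. The qualifying events are neurological, endocrine or immune: three of the four. The closing parenthesis may restrict which outcomes are analysed or which events qualify. The overlap exists on either reading.

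**3. Composite.** Let S be membership, meaning at least one of the three event types by year 3. Then P(any of the three | S) = 1 in each treatment group, and P(any impairment | S) = 1 as well. There are no non-events in either group, so the risk difference is 100% - 100% = 0 and the odds ratio has zero cells and cannot be estimated. The first composite event falls within 3 years for every member.

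One exception applies. If events after relapse or secondary malignancy can qualify a patient but are not counted, and u is the share of members with only such events, the three-domain figure is 1 - u. The protocol does not say whether they can qualify, and gives nothing from which to estimate u.

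**4. Single domains.** The following inputs are assumptions, not from the protocol: domains independent; 70% of events in each domain fall in the first 3 years; 12-year incidences a (neurological), b (endocrine) and c (immune). Then

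- P(S) = 1 - (1 - 0.7a)(1 - 0.7b)(1 - 0.7c)
- P(neurological | S) = a × [1 - 0.3(1 - 0.7b)(1 - 0.7c)] / P(S), and likewise for the other two.

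Middle scenario (a = 0.15, b = 0.30, c = 0.60): P(S) = 1 - 0.895 × 0.79 × 0.58 = 0.590. P(neurological | S) = 0.15 × (1 - 0.3 × 0.79 × 0.58) / 0.590 = 0.129 / 0.590 = 0.22.

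| Assumed whole-cohort incidence (neuro / endocrine / immune) | P(S) | Neuro in S | Endocrine in S | Immune in S |
|---|---|---|---|---|
| 15% / 30% / 90% | 74% | 19% | 37% | 96% |
| 15% / 30% / 60% | 59% | 22% | 43% | 80% |
| 10% / 15% / 30% | 34% | 23% | 34% | 66% |

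A simulation of 1,000,000 patients per scenario agrees. With neuropsychomotor incidence set at 15%, 15% and 10%, any impairment in the whole simulated cohort is 95%, 80% and 52%. In the subgroup it is 100% each time.

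**5. Neuropsychomotor impairment.** It does not define S. Under independence its incidence in S equals that in the whole cohort (10% to 15% in these scenarios).

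**6. Related subgroups.** MRD positivity at any time in years 0-3 is known only for patients who live and are tested long enough to show it, and an impairment can come before the positive test. Acute GvHD is likewise established after day 1. Neither is defined by the primary outcome, so no 100% arises. The fault there is one of timing.

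**The case against.** The strongest reply is that the protocol reports each event separately. A patient who qualifies through a low IgG need not have a neurological or endocrine disorder, and neuropsychomotor impairment is untouched by the selection. The subgroup could even show whether early neurological events precede developmental impairment. This stands, and it limits the conclusion.

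A reader might infer four stronger things that the document does not support:

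- *Every primary outcome is 100% in the subgroup.* This is true only of the any-impairment composite or the three-domain union, subject to the censoring exception.
- *All onsets fall within 3 years.* This is true only of the first composite event. Onset in a domain that did not qualify the patient can occur up to year 12.
- *Everyone outside the subgroup is free of impairment for 3 years.* Such patients may have neuropsychomotor impairment, or may have died or left before year 3.
- *The analysis is firmly planned, with a treatment odds ratio inside it.* The list is optional, and Section 9.7.2.2.3 describes the comparison for the treatment groups as a whole.

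It can also be said that landmark details belong in a statistical analysis plan. That would answer a protocol silent on the definition. This one states a definition, and the definition itself selects on the outcome.

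**Conclusion.** The definition is defective in a bounded way. For the composite, the subgroup result is fixed at 100% in both treatment groups whatever the treatment effect, except for any qualifying events left uncounted after relapse or secondary malignancy. That follows from the definitions alone. For the three qualifying domains singly, the bias is upward but short of 100%. In the illustration, neurological incidence moves from 10%-15% to 19%-23%, endocrine from 15%-30% to 34%-43%, and immune from 30%-90% to 66%-96%. Those sizes rest on assumed incidences, independence and a 70% early share. Neuropsychomotor impairment is not forced. The MRD+ and acute GvHD subgroups share the timing problem, and its size cannot be derived from the protocol. The whole-cohort analysis of the primary objective is unaffected, and because the subgroup is optional this is a wording correction to make before it is run.

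**What to change.** In Section 9.7.2.2.4, state that any subgroup classified after alloHSCT is analysed from a landmark: 3 years for the event and MRD subgroups, and a stated time for acute GvHD. Include only patients alive and in follow-up at the landmark, and classify them on data up to it. Count only outcomes with first onset after it, domain by domain, leaving a patient out of any domain already affected. Say also how patients already censored for relapse or secondary malignancy are treated, and whether an event after either can qualify a patient.

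This needs no new data. The cost is that patients who die or leave before the landmark drop out and the result applies only to those who remain. Section 9.5 assumes 35% long-term survival (52 of 149 per arm, 104 of 298 in total). Survival at year 3 is not given, but the loss may be sizeable.

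If a baseline subgroup is wanted instead, use neurological, endocrine or immune events before alloHSCT, already collected under Section 9.3.2. That keeps patients who die or leave early, but it answers a different question and is an alternative, not a repair.

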typically given throughout the course of ALL therapy starting from induction and continuing through consolidation.

Among paediatric patients with ALL, more than 95% achieve a first complete remission (CR1) with treatment and 75% to 85% remain disease-free 5 years after the initial diagnosis. Currently, about 15%-20% of patients suffer a relapse of ALL (Schrappe et al, 2013).

The prognosis for a patient with relapsed ALL mainly depends on the time elapsing from diagnosis to relapse, site of relapse, as well as cytogenetics and immunophenotype (Chessells et al, 2003; Uderzo et al, 2007; Malempati et al, 2007). The risk-group stratification of children with relapsed ALL (standard risk [SR] versus high-risk [HR] depends on time elapsing from diagnosis to relapse, and the immunophenotype (Locatelli et al, 2012).

Overall Survival (OS) rates after marrow relapse range from less than 20% for patients with marrow relapses occurring within 18 months from diagnosis to 40% to 50% for those whose relapses occur more than 36 months from diagnosis (Einsiedel et al, 2005; Nguyen et al, 2008). For patients with isolated CNS relapses, the OS rates for early relapse (< 18 months from diagnosis) are 40% to 50%, while they are 75% to 80% for children with late relapses (> 18 months from diagnosis) (Nguyen et al, 2008; Barredo et al, 2006). There is no evidence that early detection of relapse by frequent surveillance (complete blood counts or bone marrow tests) in off-therapy patients improves outcome. (Rubnitz et al, 2005). New data from the Cancer Research United Kingdom Children's Cancer Group show that approximately 50% of patients with high-risk first relapse have a second relapse within 2 years (Parker et al, 2010).

Approximately 44% of paediatric patients with second marrow relapse and 27% of those with third marrow relapse achieve a subsequent CR. Five-year disease-free survival rate in CR3 was reported to be 15% (Ko et al, 2010).

Fifteen to 20% of children with ALL die from treatment-resistant or recurrent ALL or from the acute and or long-term adverse effects of therapy (Pui and Evans, 2006; Stary et al, 2014). Two percent of children (Pui, 2008a) with ALL who do not achieve a remission are classified as having refractory disease and, often, suffer an even worse prognosis compared to patients with relapsed ALL (Schrappe et al, 2013).

7.1.2.1 Toxicity From Chemotherapy Agents Used to Treat Relapsed/Refractory Acute Lymphoblastic Leukemia

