9.2.3 Patient Eligibility

9.2.3.1 Inclusion Criteria

Patients are eligible to be included in the study if they meet all of the following inclusion criteria.

- Paediatric B-cell precursor ALL patients with any indication world-wide that received blinatumomab or chemotherapy in routine clinical practice, followed by transplantation, or EU paediatric indications that may be authorized in the future. This means that paediatric patients which receive blinatumomab off-label in the EU or with a different indication in ex-EU regions may be included in the study.
- Patient's legally acceptable representative has provided informed consent when the patient is legally too young to provide informed consent and the patient has provided written assent based on local regulations and/or guidelines prior to any study-specific activities/procedures being initiated.

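### The EU/non-EU subgroup is worded by the indication for blinatumomab and does not say that chemotherapy patients are classified, and adjustment of the regression for disease stage depends on a p<0.25 screen

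*Protocol*

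**What the plan says.** Protocol Section 9.2.3.1 admits "Paediatric B-cell precursor ALL patients with any indication world-wide that received blinatumomab or chemotherapy in routine clinical practice" who then went on to a transplant. Section 9.2.3.2 has no exclusion criteria.

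Section 9.7.2.2.4 opens with "Analyses will be undertaken for the study population as a whole and by relevant blinatumomab consolidation and chemotherapy consolidation subgroups". It then lists optional subgroups: "These subgroups may include the following (additional subgroups may be investigated"). Two entries matter here.

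- The age entry is "Age at treatment with SOC/blinatumomab by age categories", which names both treatments.
- The indication entry is "Patients with different indications for blinatumomab: EU indication" against non-EU indication, which names one treatment. The EU category is spelled out as "paediatric patients aged 1 year or older with Ph- B-cell precursor ALL which is refractory or in relapse after receiving at least 2 prior therapies"; a child whose leukaemia came back following an earlier alloHSCT also qualifies. The non-EU examples are "relapsed ALL after receiving only 1 prior therapy, ALL with MRD, Ph-positive relapsed, or refractory ALL or high-risk first relapse ALL".

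Section 9.7.2.2.3 plans one comparison of the arms, at final follow-up, if at least 50 patients per arm are enrolled and the groups are comparable. Covariates from Section 9.3.2 that differ between the arms at p<0.25 are evaluated for adjustment in the logistic or Cox model. A propensity score weighting analysis on the collected covariates is added.

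Section 9.3.2 collects disease status before blinatumomab or SOC chemotherapy. It names neither Philadelphia-chromosome status nor number of prior therapies.

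**The concern.** Each arm may mix children in first relapse or with MRD and children who are refractory, have had at least two prior therapies, or have relapsed after a transplant. The indication entry is the only listed subgroup that separates patients by disease stage before the study treatment. A chemotherapy patient was not treated under an indication for blinatumomab, so an analyst who follows the label would classify blinatumomab patients only. The EU-indication stratum would then be described in one arm, with no treatment contrast inside it.

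This matters because Sections 7.2 and 13.1 describe the study as a commitment to the EMA linked to EU approval. Section 7.1.3 gives the paediatric indication as refractory disease, relapse after at least two prior therapies, or relapse after a prior alloHSCT. The regulator can be expected to ask how the two treatments compare in those children.

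The overall comparison does not answer that question. Nor is it guaranteed to be adjusted for disease stage, which is likely to influence both the choice of treatment and the late effects. Section 9.9 confirms that covariates go into the regression models if differences are observed, so adjustment depends on a significance test of imbalance.

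**Working it through.** **Step 1: the wording.** Setting the entries of Section 9.7.2.2.4 side by side:

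| Item | Refers to | Can a chemotherapy patient be classified? |
|---|---|---|
| Age entry | SOC and blinatumomab | Yes, explicitly |
| Indication entry, label | Blinatumomab only | Not stated |
| Indication entry, EU criteria | Age, Ph status, refractory or relapsed state, prior therapies, prior alloHSCT | Yes, nothing requires receipt of blinatumomab |
| Indication entry, non-EU examples | Relapse after one therapy, MRD, Ph-positive disease, high-risk first relapse | Yes, likewise |

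The label points to one arm and the criteria fit both. No sentence in the protocol says which governs, or that the treatments are compared within each category.

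**Step 2: are the classifying variables listed?** The EU criteria need age, Ph status, refractory or relapsed state, number of prior therapies and prior alloHSCT. Section 9.3.2 lists disease status, relapse details and treatment history. Section 9.7.2.2.2 mentions prior treatments as an example of a patient characteristic. Ph status and number of prior therapies are not named, although these general items may cover part of them.

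**Step 3: can the p<0.25 screen miss an imbalance in stage?** Inputs: 50 per arm (the minimum in Section 9.7.2.2.3) and the threshold of 0.25 (same section). Assumption: 30% of one arm and 40% of the other are in the EU-type stratum; the protocol gives no stage mix.

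- Pooled proportion = (0.30 + 0.40)/2 = 0.35.
- Standard error = sqrt(2 × 0.35 × 0.65 / 50) = 0.0954.
- z = 0.10/0.0954 = 1.05, two-sided p = 0.29. A Wald test of the log odds ratio gives 0.4418/0.4226 = 1.05, p = 0.30.

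Both p-values exceed 0.25, so the stratum would not be put forward for adjustment. The two-sided 0.25 threshold is z = 1.150, so at 50 per arm imbalances up to about 1.150 × 0.0954 = 0.11, or 11 percentage points around 35%, go unflagged.

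**Step 4: the same at the target size.** With 149 per arm (Section 9.5), the standard error is sqrt(2 × 0.35 × 0.65 / 149) = 0.0553. Then z = 0.10/0.0553 = 1.81 and p = 0.07, so the 10-point imbalance is flagged. The unflagged range shrinks to about 1.150 × 0.0553 = 0.064, or 6 points. The weakness is therefore greatest if enrolment falls towards the minimum, which Section 9.5 leaves open. Even a flagged covariate is only evaluated; the text does not say that it stays in the model.

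**The case against.** The strongest reply is that this is a loose label on an optional, exploratory subgroup. The bracketed criteria are disease states, Section 9.7.2.2.4 opens by saying that analyses are done by both treatment groups, and Section 9.3.2 collects disease status before either treatment. How chemotherapy patients are classified could be settled in a statistical analysis plan, which is not shown. Disease stage is also covered by the propensity score analysis, which uses the collected covariates and is not stated to depend on the p<0.25 screen, and by the requirement that the arms be comparable.

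Much of this stands. A reader might infer that the EU-indication children have no like-for-like control. The documents do not support that: chemotherapy patients can meet the same criteria, and such patients may well be enrolled. A reader might also infer that EU-indication blinatumomab patients will be set against the whole chemotherapy arm. No section plans that contrast.

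Nor can a bias be read off the outcome figures in Section 7.1.2. They mix disease-free with overall survival and are not counted from transplant, where follow-up starts here. Their split by time to relapse is also not the EU/non-EU split, since a first relapse can fall in the non-EU category whether early or late.

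What does not stand is leaving the text alone. The protocol itself writes the subgroup with a one-arm label while the age entry names both treatments, and it fixes the screening rule for the regression. The comparability check is made across the whole arms, not within the EU-indication stratum.

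**Conclusion.** The point holds as an ambiguity in the subgroup definition together with adjustment that is not guaranteed. As worded, the EU/non-EU analysis can be carried out in the blinatumomab arm alone, and no text requires the treatments to be compared within the stratum. In the regression, disease stage and line of therapy are considered only if they pass the screen. At 50 per arm the screen overlooks imbalances up to about 11 points, and at 149 per arm up to about 6 points, assuming a stratum share near 35%.

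The effect on the impairment endpoints cannot be sized from the protocol. It gives neither the share of EU-indication patients in each arm nor impairment rates by stage. No shortage of comparable chemotherapy patients is shown, and none is claimed. The correction is cheap and worth making before data accumulate, because it also settles what must be recorded in the chemotherapy arm.

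**What to change.** 1. In Section 9.7.2.2.4, define the subgroup by disease status before blinatumomab or SOC chemotherapy, with the bracketed criteria applied identically to both arms: one stratum for patients who meet the EU criteria, one for all others. Writing out the criteria also keeps the strata stable if the EU indication is extended, which Section 9.2.3.1 foresees.
2. Report both arms within each stratum, and the adjusted treatment contrast within each stratum where numbers allow.
3. In Section 9.7.2.2.3, include this stratum as a fixed term in the logistic and Cox models and in the propensity score, whatever the result of the p<0.25 screen.
4. In Section 9.3.2, confirm that Ph status and number of prior therapies are captured in both arms.

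The cost is a few sentences and possibly two data fields. The downside is small numbers in some strata, so within-stratum contrasts may be imprecise or have to remain descriptive.
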